LAM-002A is supplied as 25 mg or 50 capsules and will be administered with a BID or TID oral dosing regimen. Subjects on a BID schedule will be advised to take the doses at the same time each day, ~12 hours apart. Subjects on a TID schedule will be advised to take the doses at the same time each day at intervals of ~6 to 8 hours. On PK days, subjects on a TID schedule should receive the morning dose and complete the blood collections through 8 hours thereafter before taking the second dose on that day. For the dose-escalation stage of the study, the dosing regimens described in Table S-1 above will be evaluated. For the cohort-expansion stage of the study, a LAM-002A starting dosing regimen of 125 mg BID will be evaluated when given as monotherapy or in combination.

Combination Therapy, Dosage and Mode of Administration:

In the expansion and extension stages (Stages 2 and 3), LAM-002A will be combined with either rituximab/rituximab hyaluronidase human or atezolizumab in cohorts of subjects as described in Table S-2 above.

For subjects allocated to LAM-002A/rituximab, the rituximab will be administered intravenously or rituximab/hyaluronidase human will be administered subcutaneously in the clinic for a total of 8 treatments:

Intravenous rituximab (Rituxan®)

- Four induction infusions of 375 mg/mg² will be administered weekly on Cycle 1 Day 1, Cycle 1 Day 8, Cycle 1 Day 15, and Cycle 1 Day 22.
- Four subsequent maintenance infusions of 375 mg/mg² will be administered every 8 weeks on Cycle 4 Day 1, Cycle 6 Day 1, Cycle 8 Day 1, and Cycle 10 Day 1.

Subcutaneous rituximab (rituximab/hyaluronidase human; Rituxan Hycela®)

- An initial dose of 375 mg/mg² will be administered intravenously on Cycle 1 Day1.
- Three subcutaneous injections of 1,400 mg/23,400 Units (1,400 mg rituximab and 23,400 Units hyaluronidase human) will be administered weekly on Cycle 1 Day 8, Cycle 1 Day 15, and Cycle 1 Day 22.
- Four subsequent maintenance subcutaneous injections of 1,400 mg/23,400 Units (1,400 mg rituximab and 23,400 Units hyaluronidase human) will be administered

Version 9, 18 Feb 2020

every 8 weeks on Cycle 4 Day 1, Cycle 6 Day 1, Cycle 8 Day 1, and Cycle 10 Day 1.

For subjects allocated to LAM-002A/atezolizumab, the atezolizumab will be administered intravenously in the clinic at a dose of 1200 mg every 3 weeks.

Duration of Treatment:

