6.8.4.2. Atezolizumab Administration

Atezolizumab will be administered intravenously in the clinic every 3 weeks. The dose for each infusion will be 1200 mg.

Using an infusion pump, atezolizumab should be administered through an intravenous line with or without a sterile, non-pyrogenic, low-protein binding in-line filter (pore size of 0.2 to 0.22 μ m). Other drugs should not be coadministered with atezolizumab through the same intravenous line.

At Cycle 1 Day 1, ~15 to 30 minutes after administration of the first dose of LAM-002A, the first infusion of atezolizumab will be administered over 60 minutes. If the first infusion is tolerated, all subsequent infusions may be delivered over 30 minutes. Atezolizumab should not be administered as an intravenous push or bolus.

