6.8.4.3. Management of Atezolizumab Infusion Toxicity

While infrequent (incident <2%), severe infusion reactions have occurred in clinical trial subjects receiving atezolizumab. For subjects with Grade 1 or 2 infusion reactions, the atezolizumab infusion should be interrupted or slowed. For subjects with Grade \geq 3 infusion reactions, atezolizumab therapy should be permanently discontinued.

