8. METHODS OF ASSESSMENT AND ENDPOINTS

All trial data during the dose-escalation stage (Stage 1) and expansion stage (Stage 2) will be recorded on the eCRFs. Timing of study procedures for the dose-escalation stage (Stage 1) and expansion stage (Stage 2) are listed in schedules of assessments tables – Table 8: Schedule of Assessments (LAM-002A Continuous Monotherapy Administration), Table 9: Schedule of Assessments (LAM-002A Intermittent Monotherapy Administration), Table 10: Schedule of Assessments (LAM-002A/Rituximab Combination Therapy), and Table 11: Schedule of Assessments (LAM-002A/Atezolizumab Combination Therapy) – in Section 8.7. During the extension stage (Stage 3), collection of clinical data by the sponsor will be limited to serious adverse event (SAE) reports. Study drug accountability will be managed per site procedures; relevant pharmacy records may be collected by the sponsor to document study drug disposition.

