- V LAM-002A to be administered to the subject in clinic (with recording of the date and actual clock time of the LAM-002A administration). On C1D1, LAM-002A will be started on a BID schedule after administration of premedications (see Section 6.8.3.1) and ~15 to 30 minutes prior to the start of the initial atezolizumab infusion. On C1D8, the morning dose of LAM-002A will be administered after premedications (see Section 6.8.3.1) and ~15 to 30 minutes prior to the atezolizumab infusion
- w Atezolizumab, 1200 mg, will be administered by intravenous infusion over ~30 minutes every 3 weeks.
- X Information on concomitant medications and other treatments will be collected from 14 days prior to informed consent through 30-37 days after the last dose of study drug.
- Y Subjects who have discontinued study treatment for reasons other than PD will be assessed at a minimum of every 12 weeks until documentation of PD, start of new anti-cancer therapy or for up to 1 year from the last enrolled subject's first treatment (C1D1) whichever comes first. Long-term follow-up survival information will be obtained in all surviving subjects who permanently discontinue study therapy. Such information may be collected at ~3- to 6-month intervals at the sponsor's discretion through 3 years. This long-term follow-up information will be gathered during routine clinic visits, other study site contact with the subjects, or via telephone or e-mail with the subjects/caregivers or referring physician offices.

Abbreviations: ALT: Alanine aminotransferase; AST: Aspartate aminotransferase; BID: twice per day; BUN: Blood urea nitrogen; CBCs: Complete blood counts; CD: Cluster of differentiation; CLL: Chronic lymphocytic leukemia; CR: Complete response; CT: Computerized tomography; ECG: Electrocardiogram; ECOG: Eastern Cooperative Oncology Group; EOT: End of treatment; FISH: Fluorescence *in situ* hybridization; F/U: Follow-up; LDH: Lactate dehydrogenase; MRI: Magnetic Resonance Imaging; PBMC: Peripheral blood mononuclear cell; PD: Progressive disease; PE: Physical exam; PET: Positron emission tomography; PK: Pharmacokinetics; QTc: Corrected QT interval; RBC: Red blood cell; SAE: Serious adverse event; T3: triiodothyronine; T4: thyroxine; TLS: tumor lysis syndrome; TSH: thyroid-stimulating hormone; WBC: White blood cell; WCBP: Women of child-bearing potential

Version 9, 18 Feb 2020

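### Table 11 footnote w sets about 30 minutes for every atezolizumab infusion, although Section 6.8.4.2 requires 60 minutes for the first; footnote V carries over rituximab wording

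*Combined protocol and SAP*

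**What the plan says.** Table 11 in Section 8.7 is the schedule for LAM-002A with atezolizumab. Its footnote w states: "Atezolizumab, 1200 mg, will be administered by intravenous infusion over ~30 minutes every 3 weeks". It neither singles out the first infusion nor makes the shorter time conditional.

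Section 6.8.4.2 says that at Cycle 1 Day 1 "the first infusion of atezolizumab will be administered over 60 minutes", and then: "If the first infusion is tolerated, all subsequent infusions may be delivered over 30 minutes".

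The synopsis gives dose and interval only: "the atezolizumab will be administered intravenously in the clinic at a dose of 1200 mg every 3 weeks". Section 9.4.5, on solution preparation, gives no infusion time either. In the text available, only Section 6.8.4.2 states the 60 minutes.

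Footnote V of Table 11 deals with in-clinic LAM-002A dosing. It begins: "On C1D1, LAM-002A will be started on a BID schedule after administration of premedications (see Section 6.8.3.1". It cites the same section for Cycle 1 Day 8, and there times the LAM-002A dose to precede an atezolizumab infusion. Section 6.8.3.1 is the rituximab premedication section: an antipyretic and an antihistamine, with an optional intravenous corticosteroid.

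**The concern.** Section 8 sends sites to these tables for timing: "Timing of study procedures for the dose-escalation stage (Stage 1) and expansion stage (Stage 2) are listed in schedules of assessments tables". A site working from Table 11 would give the first infusion in about half the specified time. It would also lose the condition that the shorter infusion depends on having tolerated the longer one.

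Both are safety provisions. Section 6.8.4.3 notes: "While infrequent (incident <2%), severe infusion reactions have occurred in clinical trial subjects receiving atezolizumab". For Grade 3 or higher it says of such events: "infusion reactions, atezolizumab therapy should be permanently discontinued". A discontinuation of that kind could also count towards the adverse-event discontinuation boundary for the atezolizumab combination in Section 14.1.2. One event alone cannot cross that boundary, whose lowest point is 3/3.

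Footnote V is a second, weaker fault. Read literally, it attaches rituximab premedication, including an optional steroid, to a drug for which Section 6.8.4.1 recommends no specific premedication and advises against systemic steroids. It also presupposes an infusion on a day when none is due.

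**Working it through.** This is a comparison of texts with a little arithmetic. The plan offers no figure of its own to reproduce.

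**First-infusion duration and rate.** The dose is 1200 mg (Section 6.8.4.2, synopsis, footnote w).

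| Source | Infusion 1 | Later infusions | Rate for infusion 1 |
|---|---|---|---|
| Section 6.8.4.2 | 60 min | 30 min if the first is tolerated | 1200 / 60 = 20 mg/min |
| Table 11 footnote w | ~30 min | ~30 min | 1200 / 30 = ~40 mg/min |

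The ratio is 40 / 20 = 2. For later infusions the two sources agree, provided the first was tolerated. The conflict is therefore confined to dose 1 and to the missing tolerance condition.

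**Whether Day 8 is an infusion day.** An interval of 3 weeks (21 days) from Day 1 gives Days 1, 1 + 21 = 22 and 22 + 21 = 43. Day 8 is not among them. Table 11's own footnotes on imaging and thyroid tests equate 4 cycles with 12 weeks, which gives 12 / 4 = 3 weeks per cycle and fits one infusion per cycle. Section 6.8.2.2 lists only the morning LAM-002A dose in the clinic on Cycle 1 Day 8 for this combination.

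**Likely origin of footnote V.** Its Day 8 sentence matches footnote v of Table 10, the rituximab schedule, with the antibody name changed. In Table 10 it is correct: rituximab is given on Cycle 1 Day 8 and does require premedication.

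**Number of subjects exposed to the error.** Table 2 plans 6 evaluable subjects in Cohort 7 and 6 in Cohort 8, so 6 + 6 = 12. This is not a ceiling, because Section 6.13 allows non-evaluable subjects to be replaced. Only subjects who had yet to receive a first infusion under Version 9 are affected. That number is not stated and could be 0.

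**Scale of the event concerned.** At the stated rate of under 2%, the expected number of severe infusion reactions in 12 subjects is below 12 × 0.02 = 0.24. This is a background expectation, not an excess caused by the footnote. The documents give no rate for a 30-minute first infusion, so no excess can be calculated.

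**The case against.** The contradiction itself is not in doubt; the dispute is over how much it matters.

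The strongest argument is that nobody may be left to be affected. Version 9 was written during the move to the extension stage, which is capped at 4 subjects already on therapy and at 2 sites. Appendix 4 records that site monitoring by the contract research organization was discontinued in that context. The expanded accrual added in Amendment 7 was for follicular lymphoma on monotherapy or with rituximab, not atezolizumab. Section 4.1.4.2 shows that some subjects had already received the atezolizumab combination. Extension-stage subjects are past their first infusion and outside the schedule tables, which Section 8 applies to Stages 1 and 2. This stands as a reason to expect few or no remaining starts. It does not settle the matter: Table 2 retains Cohorts 7 and 8, the synopsis still speaks of future subjects, and nothing states that atezolizumab accrual is closed.

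A second argument is that timing in Section 8 means the visit day rather than the infusion rate, and that a site must consult Section 6.8.4.2 to give the drug at all. That is a fair reading and lowers the chance of error. But footnote w does not leave duration to the administration section; it states one, and for the first dose it is wrong.

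Third, safeguards exist. The first 3 subjects in each combination cohort are enrolled one at a time with at least 3 weeks' observation. Infusion-related reactions are events of special interest, reportable within 24 hours. Grade 1 or 2 reactions call for slowing or interrupting the infusion. These limit the consequences but do not correct the instruction.

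On footnote V the objection largely succeeds. Footnote w's own 3-week interval, Section 6.8.2.2, the absence of a premedication row in Table 11, and the steroid restrictions in Sections 6.8.2.6.1, 6.8.4.1 and 6.9.5 make an actual Day 8 infusion or steroid premedication unlikely.

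**Conclusion.** The concern holds. In the current Version 9 text, footnote w conflicts with Section 6.8.4.2 for the first atezolizumab infusion. Followed as written, it doubles the rate from 20 to about 40 mg/min and drops the tolerance condition. Footnote V is wrong in its premedication reference and in its Day 8 infusion, with little practical consequence.

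The matter is operational and concerns safety; no endpoint, sample size or error rate changes. No increase in reactions is demonstrated or claimed.

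It should be fixed, and that rating rests on footnote w. It assumes that atezolizumab starts were still possible under Version 9, which the documents allow but do not confirm. If the sponsor confirms that none remained, it becomes a minor editorial correction.

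**What to change.** - **Footnote w:** state 1200 mg intravenously every 3 weeks, with infusion 1 over 60 minutes and later infusions over 30 minutes provided infusion 1 was tolerated, as in Section 6.8.4.2.
- **Footnote V:** delete both references to premedications and Section 6.8.3.1. Keep the Cycle 1 Day 1 timing of LAM-002A, about 15 to 30 minutes before the initial atezolizumab infusion starts. For Cycle 1 Day 8, say that only the morning LAM-002A dose is given in the clinic, as in Section 6.8.2.2.

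The cost is two footnote edits in the next amendment, using content already in the protocol. A clarification letter to sites is needed only if atezolizumab starts remain. Design, sample size and analysis are unchanged.

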9. STUDY DRUG MATERIALS AND MANAGEMENT

9.1. LAM-002A

9.1.1. Description

LAM-002A drug description is provided in Table 12.

Table 12: LAM-002A Drug Description

Product Name:	LAM-002A
Dosage Form:	Capsule
Unit Dose	25 mg or 50 mg
Route of Administration	Oral
Physical Description	Each capsule will contain 25 mg or 50 of apilimod dimesylate (equivalent to 17.1 mg or 34.3 mg of apilimod free base, respectively). The 25-mg capsule is Swedish orange and the 50-mg capsule is white. Both the 25- and 50-mg capsules are Size 0 and both have a total fill weight of 175 mg. Inactive components in active capsules are microcrystalline cellulose, silicified microcrystalline cellulose, anhydrous lactose, croscarmellose sodium, colloidal silicon dioxide, and magnesium stearate.
Manufacturer	Patheon

9.1.2. LAM-002A Packaging and Labeling

LAM-002A will be provided in bulk bottles to each investigational pharmacy for dispensing. The pharmacist will dispense capsules into bottles for each subject (based on Cohort assignment) following applicable state and federal laws and site policies. Details on the labeling, dispensing, and administration of LAM-002A are provided in the Pharmacy Manual.

9.1.3. Source

LAM-002A will be provided by the sponsor.

9.1.4. Storage

The LAM-002A must be stored in a secure storage area, with limited access, under environmental conditions appropriate for the product. LAM-002A capsules should be stored at 2 to 8°C.

9.1.5. Accountability

LAM-002A will be dispensed to subjects in labeled bottles at the beginning of each cycle. Subjects should be instructed to bring all bottles, including empty bottles, to each Day 1 or End of Treatment study visit for a compliance and product accountability check. Returned LAM-002A should be retained for monitor review prior to destruction at the site, unless contraindicated by site standard operating procedures (SOPs). If contraindicated by the site SOP,

Version 9, 18 Feb 2020

approval of site process by the sponsor must be obtained and filed in the pharmacy file and/or regulatory binder. The investigational pharmacy must maintain contemporary and accurate records on product receipt, storage temperature, stock, dispensation, return and disposal. These records should be available for review during monitoring visits and copies available for retrieval for the Trial Master File.

9.1.6. Handling and Disposal

LAM-002A accountability and inventory records will be inspected by the sponsor prior to final disposition. Instructions will be provided by the sponsor for shipment to and destruction of unused LAM-002A product by the designated packaging depot, to include unopened bulk bottles at the end of the study and expired product. Unused product returned by study subjects or opened bulk bottles will be destroyed by each site per site SOPs. LAM-002A should only be shipped or destroyed upon written authorization from the sponsor. Documentation of return of shipment, including a packing list and copy of the tracking label, should be retained in the Pharmacy and/or regulatory files.

9.2. Rituximab (for Intravenous Administration)

9.2.1. Description

Rituximab (Rituxan®, MabThera®) is a genetically engineered chimeric murine/human monoclonal IgG1 kappa antibody directed against the CD20 antigen found on pre-B and mature B cells (Genentech 2016). Rituximab is produced by mammalian Chinese hamster ovary cells. The protein has an approximate molecular weight of 145 kD.

The drug is provided as a clear, colorless, preservative-free liquid concentrate containing 10 mg/mL of rituximab. The product is formulated in 9 mg/mL sodium chloride, 7.35 mg/mL sodium citrate dihydrate, 0.7 mg/mL polysorbate 80, and water for injection with a pH of 6.5.

9.2.2. Packaging

Rituximab is supplied in 100-mg (10-mL) or 500-mg (50-mL) single-use vials.

9.2.3. Source

Unless otherwise instructed by the sponsor, the rituximab to be used in this study may be obtained from available commercial supplies.

9.2.4. Storage and Stability

Rituximab vials are stable at 2°C–8°C (36°F–46°F). Vials should be protected from direct sunlight and should not be frozen or shaken.

Diluted rituximab solutions for infusion may be stored at 2°C–8°C (36°F–46°F) for 24 hours and are known to be stable for an additional 24 hours at room temperature. However, since rituximab solutions do not contain a preservative, diluted solutions should be stored refrigerated (2°C–8°C).

No incompatibilities between rituximab and polyvinylchloride or polyethylene bags have been observed.

Version 9, 18 Feb 2020

9.2.5. Solution Preparation

Before use, the rituximab vials should be inspected for particulate matter or discoloration. Any vial with evidence of particulates or discoloration should not be used.

Using aseptic technique, the necessary amount of rituximab should be withdrawn from the vial and diluted to a final concentration of 1 to 4 mg/mL in an infusion bag containing either 0.9% Sodium Chloride, USP or 5% Dextrose in Water, USP. The bag should be gently inverted to mix the solution. The infusion solution should not be mixed or diluted with other drugs. Any unused portion of rituximab remaining in the vial should be discarded.

9.2.6. Accountability

Acquisition, storage, control, and disposal of rituximab used in the study should be performed according to institutional procedures and policies.

The investigator and/or the responsible site personnel must maintain accurate records of the source, dates of administration, quantities of administration, and lot numbers of the rituximab dispensed for this study.

9.3. Rituximab/Hyaluronidase Human (For Subcutaneous Administration)

9.3.1. Description

Rituximab/hyaluronidase human (Rituxan Hycela®) is a genetically engineered chimeric murine/human monoclonal IgG1 kappa antibody directed against the CD20 antigen found on pre-B and mature B cells. In this formulation, it is combined with hyaluronidase human, an endoglycosidase (Genentech 2018). Rituximab is produced by mammalian Chinese hamster ovary cells. The protein has an approximate molecular weight of 145 kD. Hyaluronidase human increases permeability of the subcutaneous tissue by temporarily depolymerizing hyaluronan.

The drug is provided as a colorless to yellowish, clear to opalescent, preservative-free liquid solution. Each mL of solution contains rituximab (120 mg), hyaluronidase human (2,000 Units), L-histidine (0.53 mg), L-histidine hydrochloride monohydrate (3.47 mg), L-methionine (1.49 mg), polysorbate 80 (0.6 mg), α,α-trehalose dihydrate (79.45 mg), and Water for Injection.

9.3.2. Packaging

For use in patients with FL/DLBCL, rituximab/hyaluronidase human is supplied in single-dose vials containing 1,400 mg rituximab and 23,400 Units hyaluronidase human per 11.7 mL of solution.

9.3.3. Source

Unless otherwise instructed by the sponsor, the rituximab/hyaluronidase human to be used in this study may be obtained from available commercial supplies.

9.3.4. Storage and Stability

Rituximab/hyaluronidase human vials are stable at 2°C-8°C (36°F-46°F). Vials should be protected from direct sunlight and should not be frozen or shaken.

Version 9, 18 Feb 2020

Diluted rituximab/hyaluronidase human solutions for injection may be stored at 2°C-8°C (36°F-46°F) for 48 hours and are known to be stable for an additional 8 hours at room temperatures up to 30°C (86°F) in diffuse light. However, since rituximab solutions do not contain a preservative, solutions should be used as soon as possible after withdrawal from the vial.

Rituximab/hyaluronidase is compatible with polypropylene and polycarbonate syringe material and stainless-steel transfer and injection needles.

9.3.5. Preparation

Before use, the rituximab/hyaluronidase human vials should be inspected for particulate matter or discoloration. Any vial with evidence of particulates or discoloration should not be used.

Using aseptic technique, the entire 11.7 mL of rituximab/hyaluronidase human should be withdrawn from the vial via a hypodermic needle into a syringe and the vial should be discarded.

9.3.6. Accountability

Acquisition, storage, control, and disposal of rituximab/hyaluronidase used in the study should be performed according to institutional procedures and policies.

The investigator and/or the responsible site personnel must maintain accurate records of the source, dates of administration, quantities of administration, and lot numbers of the rituximab/hyaluronidase dispensed for this study.

9.4. Atezolizumab

9.4.1. Description

Atezolizumab (TECENTRIQ®) is an Fc-engineered, humanized, monoclonal antibody that binds to PD-L1 and blocks interactions with the PD-1 and B7.1 receptors (Genentech 2017). Atezolizumab is a non-glycosylated IgG1 kappa immunoglobulin that has a calculated molecular mass of 145 kDa.

The drug is provided as a sterile, preservative-free, colorless to slightly yellow solution in single-dose vials. Each mL of TECENTRIQ contains 60 mg of atezolizumab and is formulated in glacial acetic acid (16.5 mg), L-histidine (62 mg), sucrose (821.6 mg), polysorbate 20 (8 mg). The solution has a pH of 5.8.

